9.5.1 Pneumonitis

- For Grade 2 events, treat with systemic corticosteroids. When symptoms improve to Grade 1 or less, steroid taper should be started and continued over no less than 4 weeks.
- For Grade 3-4 events, immediately treat with intravenous steroids. Administer additional anti-inflammatory measures, as needed.
- Add prophylactic antibiotics for opportunistic infections in the case of prolonged steroid administration.

9.5.2 Diarrhea/colitis

Patients should be carefully monitored for signs and symptoms of enterocolitis (such as diarrhea, abdominal pain, blood or mucus in stool, with or without fever) and of bowel perforation (such as peritoneal signs and ileus).

All patients who experience diarrhea/colitis should be advised to drink liberal quantities of clear fluids. If sufficient oral fluid intake is not feasible, fluid and electrolytes should be substituted via IV infusion.

- For Grade 2 or higher diarrhea, consider GI consultation and endoscopy to confirm or rule out colitis.
- For Grade 2 diarrhea/colitis, administer oral corticosteroids.
- For Grade 3 or 4 diarrhea/colitis, treat with intravenous steroids followed by high dose oral steroids.
- When symptoms improve to Grade 1 or less, steroid taper should be started and continued over no less than 4 weeks.

9.5.3 Type 1 Diabetes Mellitus

if new onset, including diabetic ketoacidosis [DKA]) or \geq Grade 3 Hyperglycemia, if associated with ketosis (ketonuria) or metabolic acidosis (DKA)

For **T1DM** or **Grade 3-4** Hyperglycemia:

- Insulin replacement therapy is recommended for Type I diabetes mellitus and for Grade 3-4 hyperglycemia associated with metabolic acidosis or ketonuria.
- Evaluate patients with serum glucose and a metabolic panel, urine ketones, glycosylated hemoglobin, and C-peptide.

9.5.4 Hypophysitis

- For **Grade 2** events, treat with corticosteroids. When symptoms improve to Grade 1 or less, steroid taper should be started and continued over no less than 4 weeks. Replacement of appropriate hormones may be required as the steroid dose is tapered.
- For **Grade 3-4** events, treat with an initial dose of IV corticosteroids followed by oral corticosteroids. When symptoms improve to Grade 1 or less, steroid taper should be started and continued over no less than 4 weeks. Replacement of appropriate hormones may be required as the steroid dose is tapered.

9.5.5 Hyperthyroidism or hypothyroidism

Thyroid disorders can occur at any time during treatment. Monitor patients for changes in thyroid function (at the start of treatment, periodically during treatment, and as indicated based on clinical evaluation) and for clinical signs and symptoms of thyroid disorders.

- **Grade 2** hyperthyroidism events: non-selective beta-blockers (e.g. propranolol) are suggested as initial therapy.
- **Grade 3-4** hyperthyroidism treat with an initial dose of IV corticosteroid followed by oral corticosteroids. When symptoms improve to Grade 1 or less, steroid taper should be started and continued over no less than 4 weeks. Replacement of appropriate hormones may be required as the steroid dose is tapered.
- **Grade 2 – 4** hypothyroidism, thyroid hormone replacement therapy, with levothyroxine or liothyronine, is indicated per standard of care.

9.5.6 Hepatic

- For **Grade 2** events, monitor liver function tests more frequently until returned to baseline values (consider weekly).
- Treat with IV or oral corticosteroids
- For **Grade 3-4** events, treat with intravenous corticosteroids for 24 to 48 hours.
- When symptoms improve to Grade 1 or less, a steroid taper should be started and continued over no less than 4 weeks.

9.5.7 Renal failure or nephritis

- For **Grade 2** events, treat with corticosteroids.
- For **Grade 3-4** events, treat with systemic corticosteroids.
- When symptoms improve to Grade 1 or less, steroid taper should be started and continued over no less than 4 weeks.

9.5.8 Rash

- **Grade 2:** Treat symptomatically with topical steroid cream, as well as antihistamines (i.e., loratadine, diphenhydramine, etc.). For patients that do not respond, consider starting steroids at 0.5 mg/kg prednisone or equivalent.
- **Grade 3:** As above for grade 2 and Start steroids at 1 mg/kg prednisone or equivalent.
- If any signs of Steven Johnson Syndrome (SJS) or Toxic Epidermal Necrolysis (TENS), immediately hospitalize patient and treat with high dose IV steroids (1-gram methylprednisolone) and consult dermatology.

9.5.9 Management of Infusion Reactions:

Signs and symptoms usually develop during or shortly after drug infusion and generally resolve completely within 24 hours of completion of infusion.

Table 9.21 below shows treatment guidelines for subjects who experience an infusion reaction associated with administration of durvalumab.

Table 9.21 Infusion reaction treatment guidelines as per standard care are included in the appendix.

10.0 Adverse Event (AE) Monitoring and Reporting

This study is monitored by internal oversight specialists at the University of Iowa. The Data and Safety Monitoring Plan of the Holden Comprehensive Cancer Center provides standard operating procedures to monitor all investigator-initiated trials at UIHC by the Data and Safety Monitoring Committee (DSMC). A copy of the detailed data and safety monitoring plan for this study is on file with the Data and Safety Monitoring Committee of the Holden Comprehensive Cancer Center and the IRB of record; an abbreviated copy is provided (Appendix).

This study has been assigned as a risk level 4 as it utilizes an investigator sponsored IDE [[name], MD, sponsor].

10.1 Definitions

10.1.1 Adverse Event [durvalumab]

Any untoward medical occurrence or undesirable event experienced in a subject of a clinical investigation that associated with the use of a drug in humans, whether or not considered drug related. Note: this term is for study drug and not the study device

10.1.2 Suspected Adverse Reaction [durvalumab]

Any adverse event for which there is a reasonable possibility that the drug caused the adverse event. For the purposes of safety reporting, "reasonable possibility" means there is evidence to suggest a causal relationship between the drug and the adverse event. Suspected adverse reaction implies a lesser degree of certainty about causality than adverse reaction, which means any adverse event caused by a drug. [21CFR§312.32(a)]

10.1.3 Unexpected adverse event or unexpected suspected adverse reaction [durvalumab]

An adverse event or suspected adverse reaction is considered "unexpected" if it is not listed in the investigator brochure or is not listed at the specificity or severity that has been observed; or, if an investigator brochure is not required or available, is not consistent with the risk information described in the general investigational plan or elsewhere in the current application, as amended. For example, under this definition, hepatic necrosis would be unexpected (by virtue of greater severity) if the investigator brochure referred only to elevated hepatic enzymes or hepatitis. Similarly, cerebral thromboembolism and cerebral vasculitis would be unexpected (by virtue of greater specificity) if the investigator brochure listed only cerebral vascular accidents. "Unexpected," as used in this definition, also refers to adverse events or suspected adverse reactions

that are mentioned in the investigator brochure as occurring with a class of drugs or as anticipated from the pharmacological properties of the drug but are not specifically mentioned as occurring with the particular drug under investigation. [21CFR§312.32(a)]

10.1.4 Serious Adverse Event [durvalumab]

Per 21CFR§312.32, an adverse event is considered serious if, in the view of the investigator, the adverse event results in any of the following outcomes:

- Death,
- A life-threatening adverse event,
- An inpatient hospitalization or a prolongation of existing hospitalization,
- A persistent or significant incapacity or substantial disruption of the ability to conduct normal life functions,
- A congenital anomaly/birth defect, or,
- An important medical event that may jeopardize the subject and may require medical or surgical intervention to prevent one of the other outcomes listed in this definition

10.1.5 Serious Adverse Reaction [durvalumab]

A serious adverse event for which there is a reasonable possibility that the drug caused the serious adverse event.

10.1.5 Adverse effect [90Y TheraSpheres]

Any adverse medical occurrence that may or may not be related to the investigational device

10.1.6 Unanticipated Adverse Device Effect (UADE) [90Y TheraSpheres]

Any serious adverse effect on health or safety or any life-threatening problem or death caused by, or associated with, a device, if that effect, problem, or death was not previously identified in nature, severity, or degree of incidence in the investigational plan or application (including a supplementary plan or application), or any other unanticipated serious problem associated with a device that relates to the rights, safety, or welfare of subjects [21CFR§812.3(s)]

10.1.7 Attribution to durvalumab or 90Y-TheraSpheres

When assessing whether an adverse event (AE) is related to durvalumab or an adverse effect is related to 90Y-TheraSpheres, the following attribution categories are utilized:

- Definite - The AE is *clearly related* to the agent(s)/procedure.
- Probable - The AE is *likely related* to the agent(s)/procedure.
- Possible - The AE *may be related* to the agent(s)/procedure.
- Unlikely - The AE is *doubtfully related* to the agent(s)/procedure.
- Unrelated - The AE is *clearly NOT related* to the agent(s)/procedure.

10.2 Determination of Reporting Requirements

Toxicity will be graded according to NCI's Common Toxicity Criteria (CTCAE v5). The principal investigator will have final responsibility for determining the attribution of toxicity as it is related to durvalumab. The IDE sponsor will have final responsibility for determining the attribution of toxicity as it is related to 90Y-TheraSpheres.

The clinical research team is responsible for collecting and recording the research data. As these results are collected, all toxicities and adverse events will be identified and reported to the principal investigator (PI). The principal investigator (PI) will determine final relationship of the event to the investigational product (ascorbate):

- Grade 1 and 2 events do not require attributions assigned.
- Grade 3 and higher adverse events require attribution assigned to durvalumab and 90Y TheraSpheres.
- All serious adverse events, regardless of severity, require attribution assigned to durvalumab and 90Y TheraSpheres.
- All dose limiting toxicities, regardless of severity, require attribution assigned to durvalumab and 90Y TheraSpheres.

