2.2 Secondary Goals*

2.2.1 To report **treatment related adverse events** in patients treated with the combination treatment of Y90-RE and durvalumab as assessed by Common Toxicity Criteria for Adverse Events (CTCAE) version 5.0

2.2.2 To determine the **Recommended Phase II dose (RP2D)** of durvalumab in combination with Y90-RE to treat liver-predominant mCRC.

2.2.3 To determine the efficacy of combination treatment of Y90-RE and durvalumab in patients with liver-predominant mCRC measured by overall response rate (**ORR**) (complete response (CR) + partial response (PR)) post-Y90-RE and immunotherapy.

2.2.4 To determine the efficacy of combination treatment of Y90-RE and durvalumab in patients with liver-predominant mCRC measured by the disease control rate (**DCR**) (CR+PR+stable disease (SD)) at 2 months post-Y90-RE treatment.

2.2.5 To determine the efficacy of the regimen in the treated liver metastases (liver-specific progression free survival (**Liver-PFS**) in the lesions in the Y90-RE field).

2.2.6 To determine the efficacy of the regimen in the patient as a whole (**PFS**); including both Y90-RE field and outside the Y90-RE field.

- 2.2.7 To determine the efficacy of combination treatment of Y90-RE and durvalumab in subject with liver-predominant mCRC as measured by overall survival (**OS**) at 1-year and 2-year.
- 2.2.8 To determine duration of response (**DOR**) in the Y90-RE field and outside of Y90-RE field
 - * *Given Y90-RE to the liver and use of immunotherapy, all response assessments by modified RECIST (mRECIST) as well as immune RECIST (iRECIST). In all instances, the landmark time is the initiation of immunotherapy.*

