8.1 Treatment schedule modifications in patients based on adverse events

Patients will be evaluated by the study team prior to each dose of durvalumab for an adverse event check. Determination will be made if the adverse event is treatment-related (possible, probable or definite), i.e. a toxicity (see Section 10; Adverse event monitoring and reporting). If any adverse event has occurred, then the treatment schedule will be modified as in Section 8.2.

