17.5.2 Toxicity Profile

The term toxicity is defined as adverse events that are classified as either possibly, probably, or definitely related to study treatment. Non-hematologic toxicities will be evaluated via the ordinal CTC standard toxicity grading. Hematologic toxicity measures of thrombocytopenia, neutropenia, and leukopenia will be assessed using continuous variables as the outcome measures (primarily nadir) as well as categorization via CTC standard toxicity grading.

Overall toxicity incidence as well as toxicity profiles by dose level, patient and tumor site will be explored and summarized. Frequency distributions, graphical techniques and other descriptive measures will form the basis of these analyses.

Please note for the response/efficacy evaluation, it will be mRECIST as well as iRECIST that will be reported. A confirmatory scan can be done 4 weeks post completion of therapy if there are clinical concerns.

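### Section 10.2 waives attribution for non-serious, non-DLT Grade 1-2 events, but 17.5.2 and goal 2.2.1 report related events with no grade floor, so the low-grade treatment-related summary may be incomplete

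*Combined protocol and SAP*

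**What the plan says.** Section 10.2 sets the attribution duty by grade and type of event. Grade 3 and higher events must be attributed to both agents. For the lower grades, "Grade 1 and 2 events do not require attributions assigned". Two exceptions apply at any grade: "All serious adverse events, regardless of severity, require attribution assigned to durvalumab and 90Y TheraSpheres", and "All dose limiting toxicities, regardless of severity, require attribution assigned to durvalumab and 90Y TheraSpheres". On who decides, the section gives the principal investigator (PI) the final word for durvalumab, and then "The IDE sponsor will have final responsibility for determining the attribution of toxicity as it is related to 90Y-TheraSpheres". The sentence that introduces the bullets, however, names the PI alone and calls the product ascorbate, which is not an agent in this trial.

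The analysis plan depends on attribution. In 17.5.2, "The term toxicity is defined as adverse events that are classified as either possibly, probably, or definitely related to study treatment". The same section adds that "Non-hematologic toxicities will be evaluated via the ordinal CTC standard toxicity grading", and it plans overall incidence and profiles by dose level. Goal 2.2.1, first among the secondary goals, is to report "treatment related adverse events" under CTCAE version 5.0. Neither text restricts the grades.

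Section 8.1 describes an adverse event check before each durvalumab dose: "Determination will be made if the adverse event is treatment-related (possible, probable or definite), i.e. a toxicity". It then refers the reader to Section 10. Section 17.5.1 separately tabulates all adverse events whatever their cause.

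**The concern.** Two parts of one plan pull against each other. The analysis sorts events by a variable that the data-collection rule does not ask for in non-serious Grade 1-2 events that are not DLTs. Attribution would then be optional, left to whoever records the event. A table of related events built on it could omit related low-grade events, or include them only where someone chose to judge them.

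At stake is the low-grade part of the report that answers goal 2.2.1. The all-cause table cannot stand in for it, because that goal asks specifically about events related to treatment. If the gap is found only at analysis, attribution would have to be made in retrospect, with dose level and outcome known.

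**Working it through.** **1. The plan's own figure.** The only stated number that rests on the word toxicity is in 17.2: the chance of seeing, among six patients at the MTD, a toxicity with 25% incidence. 1 - (1 - 0.25)^6 = 1 - 0.178 = 0.822, which agrees with the stated 82%. That arithmetic is right and nothing here changes it.

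**2. Collection rule against analysis rule.**

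| Class of event | Attribution required by 10.2 | Counted under 17.5.2 and 2.2.1 if related |
|---|---|---|
| Grade 3 and higher | Yes, both agents | Yes |
| SAE, any grade | Yes, both agents | Yes |
| DLT, any grade | Yes, both agents | Yes |
| Grade 1-2, neither SAE nor DLT | No | Yes |

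Only the last row conflicts. The absence of a grade limit in 17.5.2 cannot be assumed to mean Grade 3+, because 17.5.1 singles out Grade 3+ events explicitly where it wants them.

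**3. Does another section supply the missing duty?**
- 8.1 requires a relatedness judgment at any grade, but only at pre-dose checks, and it points back to Section 10.
- 9.5 sets a presumption for potentially immune-related events only.
- 10.1.7 lists the attribution categories without saying which events must receive one.
- 10.2.2 provides a two-year record review for radiation-induced events only.
- 10.5.1 and 10.5.2 send routine events to OnCore for review and assessment. The attribution scale appears in 10.5.1 inside the definition of an adverse event, not as an instruction to assign it.
- 4.1 schedules adverse event assessment at every cycle and at the end-of-treatment visit, so events are captured, but it does not mention attribution.

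Together these give partial cover. None requires every Grade 1-2 event to be attributed to both agents.

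**4. How far 8.1 reaches after radioembolization.** From the dose table in 7.4.1, durvalumab doses after Y90-RE equal total doses minus the two given before it: level 1, 2 - 2 = 0; level 2, 3 - 2 = 1; level 3, 4 - 2 = 2; level 4, 5 - 2 = 3. At levels -1 and -2 all doses come after Y90-RE, giving 2 and 1. The second dose must precede Y90-RE even on the same day (4.1, footnote 9). At the starting level, therefore, no 8.1 check follows Y90-RE. At every level, events first seen after the last dose fall outside 8.1.

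**5. Size.** For one event term, let r of n patients have an event labelled related, and let u further patients have only unattributed Grade 1-2 events of that term. The related incidence then lies between r/n and (r + u)/n, a width of u/n. The documents give neither u nor a Grade 1-2 event rate for this combination from which to estimate it. The shortfall could be anything from none of the related low-grade events to all of them.

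**The case against.** The strongest reply is that a waiver is not a ban. The opening of 10.2 gives the PI and the IDE sponsor final responsibility for attribution with no grade limit, and 8.1 creates a positive duty in the same related categories that 17.5.2 uses. The Data Submission Schedule, the OnCore forms and the full monitoring plan are not in the documents and may already call for attribution at every grade. Section 17.5 also treats all results as exploratory. Much of this stands: the summary may be incomplete, but it cannot be said that it will be. It does not remove the conflict, because the bullets in 10.2 state when attribution is required and the first one exempts Grade 1-2.

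Four stronger readings are tempting and are not supported.
- A reader might infer that an unlabelled event could mean either unrelated or never judged. Section 10.1.7 has Unlikely and Unrelated categories, so an event judged unrelated carries a label and a blank is identifiable as not attributed.
- The counts of 0 to 3 post-Y90-RE checks might suggest that labelling will differ by dose level. They show unequal opportunity under 8.1. Uneven labelling itself is possible but not shown.
- Nine of the ten event categories in Table 8.21 have a row that acts at Grade 1 or 2. This shows that durvalumab-relatedness has to be judged at low grades for dosing; it does not measure missing attribution.
- One unattributed patient widens the incidence range by 1/18 = 5.6 points, or by 1/6 = 16.7 points in a dose level of six. That is true of any missing yes/no item and says nothing about how many will be missing here.

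**Conclusion.** The plan contradicts itself as written: a stated collection rule withholds, for one class of events, the variable that a stated secondary goal needs. The consequence is conditional. If 10.2 is followed literally and the unseen forms do not ask for more, the Grade 1-2 part of the treatment-related summary may be incomplete or selectively labelled, to an extent the documents do not allow anyone to state.

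The reach is narrow. Grade 3+ events, SAEs, DLT and MTD decisions, hematologic nadirs and the all-cause tables of 17.5.1 do not depend on the waived attributions. No sample size or error rate changes, and the analysis is descriptive. This is a minor point. Confidence is high in the conflict of wording and lower in its practical effect.

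**What to change.** In 10.2, replace the four bullets with one rule, for example: *Every adverse event, whatever its grade or seriousness, is attributed to durvalumab by the PI and to 90Y TheraSpheres by the IDE sponsor, using the categories in 10.1.7.* Correct the sentence that introduces the bullets, so that it no longer names ascorbate or the PI alone. Leave the expedited-reporting thresholds and the 8.1 pre-dose check as they are, so that no dosing decision is made to wait for final attribution.

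The text change is small. The running cost is two attributions for each non-serious Grade 1-2 event in about 18 patients. The documents do not say whether OnCore already has the fields.

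If the waiver is kept instead, say in 17.5.2 and 2.2.1 that treatment-related summaries cover only Grade 3+ events, SAEs and DLTs, and that other Grade 1-2 events are reported all-cause under 17.5.1. This costs only text, but gives up treatment-related reporting at low grades. Either choice should be made before data accrue.

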10.2.1 Exemption from reporting requirements

The following hospitalizations are exempted from reporting because there is no “adverse event” (*i.e.*, there is no untoward medical occurrence) associated with the hospitalization:

- Hospitalizations for respite care
- Planned hospitalizations required by the protocol
- Hospitalization planned before informed consent (where the condition requiring the hospitalization has not changed post study drug administration)
- Hospitalization for elective procedures unrelated to the current disease and/or treatment on this trial
- Hospitalization for administration of study drug or insertion of access for administration of study drug
- Hospitalization for routine maintenance of a device (*e.g.*, battery replacement) that was in place before study entry

10.2.2 Reporting window

The adverse event collection window is from the first treatment (durvalumab or TheraSphere) through 30 days after the final administration (durvalumab or TheraSphere). Medical records and study records will be reviewed for up to 2 years post-embolization for radiation-induced adverse events. These will be assessed by the IDE-sponsor or delegate and captured in the electronic data capture system.

